### 9.7.1.4.2. Laboratory Values

By-visit tabular summaries of the laboratory test results will be presented. For quantitative laboratory tests, both actual values and change from screening values will be summarized.

Laboratory test results will be assigned an LNH classification according to whether the value was below (L), within (N), or above (H) the laboratory parameter's reference ranges provided by the central laboratory. Within treatment comparisons will be based

on 3 by 3 tables (shift tables) that, for a particular laboratory test, compare the LNH classification at screening to the LNH classification and the Final Visit.

#### 9.7.1.5. Vital Signs

By-visit tabular summaries of the actual vital sign, height, and weight measurements and the changes from baseline will be presented.

### 9.7.1.6. ECG Results

By-visit tabular summaries of the quantitative ECG parameters and the overall ECG findings (normal, abnormal not clinically significant, or abnormal clinically significant) will be presented. For the quantitative ECG parameters, both actual values and change from screening values will be summarized.

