## 7. INTRODUCTION

Viloxazine was previously marketed as an antidepressant in several European countries, since the 1970's, and is currently under development by the Sponsor as SPN-812V, for its potential utility in treating adult attention deficit hyperactivity disorder (ADHD). Viloxazine is a racemate and Supernus plans to develop the compound as such. Supernus intends to carry out this preliminary safety and proof of concept study in adult ADHD patients using an immediate release formulation that will support future development of a modified release formulation to facilitate compliance and possibly improve tolerability.

Similar to tricyclic antidepressants and atomoxetine, viloxazine is an inhibitor of the reuptake of norepinephrine, but may also enhance the release of serotonin from neuronal stores. Clinical efficacy in Major Depressive Disorder has been shown at daily doses of 300 to 600 mg. Thorough published pharmacological and clinical summaries of the product are found in the reviews of Pinder et al., 1977 and Ban et al., 1980.

Supernus development thesis is based on the current unmet medical need for effective longacting non-stimulant treatment for ADHD in adults. Viloxazine can offer a compelling alternative to the use of scheduled substances to control ADHD thus limiting patients' exposure to agents with potential for substance abuse. This Phase I/IIa study seeks to evaluate the safety and tolerability of an immediate release formulation of viloxazine given three times per day (TID) at a dose of 150 or 300mg/day in adults. A randomized, multicenter, parallel group, double-blind, placebo-controlled dose-ranging study design will be used. 50 subjects will be randomized; assuming a 20% dropout rate, it is anticipated that 40 subjects will complete the study. Subjects will be monitored regularly for safety endpoints.

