## 9.3.1 Inclusion Criteria

Subjects meeting all of the following criteria may be included in the study:

- 1. Able to provide informed consent prior to any study procedure being conducted.
- 2. Capable and willing to comply with study procedures.
- 3. Male or female aged 18 to 64, inclusive.
- 4. Subjects with a current diagnosis of ADHD as confirmed by the Conners' Adult ADHD Diagnostic Interview for DSM-IV (CAADID)
- 5. Clinical Global Impression Severity (CGI-S) score of 4 or higher.
- 6. On no treatment for ADHD or willing to be withdrawn from an ongoing treatment after a washout of at least 10 days.
- 7. Body Mass Index (BMI) between 18.0 and 34.0 inclusive
- 8. Subject must be in general good health as determined by medical history, ECG, and other analysis that, in the judgment of the Investigator, would confirm the Subject's good health.
- 9. Females of childbearing potential (FOCP) who, if sexually active, agree to use acceptable forms of contraception (including oral, transdermal, or implanted contraceptives; intrauterine device; female condom with spermicide; diaphragm with spermicide; cervical cap; abstinence; use of condom with spermicide by sexual partner or sterile [at least 6 months prior to SM administration] sexual partner) at least 14 days prior to start of study drug administration, throughout the study, and for 30 days following the last dose of SM.
- 10. Postmenopausal females with amenorrhea for at least 2 years or females who are permanently sterilized (e.g., tubal occlusion, hysterectomy, bilateral salpingectomy).

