## 9.4.4.3. Laboratory Measurements

Clinical laboratory tests will be performed by a central laboratory. Information regarding collecting, handling, and shipping samples will be detailed in a separate manual. The Schedule of Visits and Procedures (Table 1. Schedule of Visits and Procedures) shows the time points at which blood and urine will be collected for clinical laboratory tests.

For subjects who participate in the optional PK portion of the study, a total of approximately 32mL (8 PK blood draws  $\times$  4mL) of blood/subject will be taken during the course of the study for the purpose of PK samples, in addition to 29mL (2 blood draws for clinical chemistry  $\times$  14.5mL) required for laboratory tests for all subjects. A complete list of all clinical laboratory assessments is presented in Table 2. Clinical Laboratory Assessments.

Laboratory personnel contact information and laboratory sample shipment information and instructions are listed in the Site Manual and/or Regulatory Binder provided to each investigational site.

Hematology	Serum Chemistry	Urinalysis			
Hematocrit Hemoglobin Red blood cell count (RBC) Platelet count White blood cell count (WBC) (with differential)	Albumin Alkaline phosphatase Alanine transaminase (ALT) Aspartate transaminase (AST) Bilirubin- Total and Direct Blood urea nitrogen (BUN) Calcium Chloride Cholesterol- Total, HDL and LDL Creatinine Creatine phosphokinase (CPK) Gamma-glutamyl transpeptidase (GGT)	Ketones Protein Specific gravity Glucose pH			
	Glucose Inorganic phosphorous Potassium Sodium Total protein Triglycerides Uric acid				
Other tests					
	ouse (amphetamines, barbiturates done, opiates, phencyclidine, proj ?)				

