# 9.4.4.6. Electrocardiograms (ECGs)

ECGs (12-lead) will be obtained at the Screening Visit, Visit 4, and the Final Visit as designated on the Schedule of Visits and Procedures (Table 1. Schedule of Visits and Procedures). Additional ECGs may be performed at other times if deemed necessary.

The ECG will be recorded while the subject is resting in a supine position. The ECG will electronically measure the PR, QRS, QT, and QTc intervals, and heart rate.

All ECG tracings will be reviewed within 24 hours by the Investigator or qualified Sub-Investigator. PR intervals will be determined for each of these ECGs from a single reading. Invalid measurements will be repeated. QTc will be reported as QTcF (QT corrected using Fridericia's method).

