#### 5.1 GENERAL CONSIDERATIONS AND STATISTICAL/ANALYTICAL ISSUES

#### 5.1.1 **Definition of Baseline**

Unless stated otherwise, subject's Visit 2 will be considered as Baseline for statistical analyses. If subject's Visit 2 assessment is missing, the last available value on or prior to the first study dose date will be used as baseline.

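### ECG and laboratory baselines come from screening and are not tied to the ADHD-drug washout, so within-arm changes and QTcF outlier counts may carry a washout effect; the placebo comparison stays unbiased in expectation

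*Protocol*

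**What the plan says.** - **Reference value, protocol.** For ECGs (9.7.1.6): "For the quantitative ECG parameters, both actual values and change from screening values will be summarized". For laboratory tests (9.7.1.4.2): "For quantitative laboratory tests, both actual values and change from screening values will be summarized".
- **Timing of measurements.** Protocol 9.4.4.6: "ECGs (12-lead) will be obtained at the Screening Visit, Visit 4, and the Final Visit". Table 1 places hematology and chemistry at screening and end of study only, and 9.4.4.3 budgets for "2 blood draws for clinical chemistry". The Visit 2 procedures in 9.4.1.2 include vital signs and weight but no ECG or safety laboratory test.
- **Reference value, SAP.** Section 5.1.1 begins: "Unless stated otherwise, subject's Visit 2 will be considered as Baseline for statistical analyses". If that value is missing, "the last available value on or prior to the first study dose date will be used as baseline".
- **Washout.** Inclusion criterion 6 (Protocol 9.3.1) admits a subject who is "On no treatment for ADHD or willing to be withdrawn from an ongoing treatment after a washout of at least 10 days". Under 9.1.1, consent precedes every assessment, screening falls within 14 days before randomization, and it may be spread over more than one visit.
- **Where the baseline is used.** The synopsis lists ECG and laboratory changes both within treatment (safety items 2 and 6) and against placebo (items 3 and 7). Protocol 9.7.1.4.2 describes the laboratory shift tables as within-treatment comparisons. SAP 6.4 plans ECG change, ECG shift and a count of subjects whose QTcF rises by 60 msec or more (Tables 14.3.5.2 to 14.3.5.4).

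**The concern.** Safety is the primary objective, and a change from baseline is informative only if the baseline reflects the untreated state. A subject who consents while taking an ADHD drug and has the ECG and blood draw that same day contributes an on-drug baseline. The later change then combines two things: loss of the prior drug and exposure to study medication.

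The protocol's introduction gives a reason to take this seriously for some prior drugs: "Similar to tricyclic antidepressants and atomoxetine, viloxazine is an inhibitor of the reuptake of norepinephrine". If a prior drug and the study drug moved an ECG interval the same way, an on-drug baseline would understate the study drug's effect in that subject. If they moved it in opposite directions, the effect would be overstated. A reader looking at one arm, a shift table or a single outlier could not tell a washout effect from a study-drug effect.

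**Working it through.** The plan states no figure on this point, so there is none to reproduce. The check has four parts.

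**1. Which value becomes baseline?** The protocol names screening. The SAP names Visit 2, where no ECG or safety laboratory test is scheduled, so its fallback applies: the last value up to the first dose date. On the planned schedule that is also a screening-period value. A repeat test or extra ECG taken later in screening would replace it, but none is required.

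**2. Can that value be on-drug?** Inputs: a screening window of up to 14 days and a washout of at least 10 days, taken here to be complete by Visit 2.
- A washout started during screening must begin by about day −10. Slack in the window: 14 − 10 = 4 days.
- An ECG or blood draw between day −14 and about day −10 can therefore be on-drug. A later one can fall during the washout.
- Conversely, a subject who stops on day −14 completes 10 days on day −4, leaving up to 4 days for a post-washout measurement.

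A pre-washout baseline is thus possible but not mandated, and a post-washout baseline is feasible but not required.

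**3. Effect on mean changes.** Let p be the share of an arm with an on-drug baseline, w the shift in the parameter caused by washout, and n the number per arm. The documents give neither p nor w; p = 10% to 50% is an assumption.
- Shift in one arm's mean change = p × w.
- Expected shift in the difference between arms = p × w − p × w = 0, because the washout precedes dosing in both randomised arms.
- SD of the chance imbalance = w × √(2p(1 − p)/n). For p = 0.30 and n = 25: w × √(2 × 0.30 × 0.70/25) = w × √0.0168 = 0.130w.

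| Assumed p | Shift in each arm's mean | Imbalance SD, n = 25 | 95% range, n = 25 | Imbalance SD, n = 20 |
|---|---|---|---|---|
| 10% | 0.10w | 0.085w | ±0.17w | 0.095w |
| 30% | 0.30w | 0.130w | ±0.25w | 0.145w |
| 50% | 0.50w | 0.141w | ±0.28w | 0.158w |

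The n = 20 column reflects the protocol's 40 anticipated completers. A simulation of 200,000 draws per case gave a mean difference of zero to three decimals and the same SDs to within 0.001.

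For illustration only, take w as 5 to 10 msec in size. Each arm's mean would shift by between 0.10 × 5 = 0.5 and 0.50 × 10 = 5 msec. The imbalance SD would run from 0.085 × 5 = 0.4 to 0.141 × 10 = 1.4 msec.

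**4. Effect on a single subject.** Observed change = true change + w. On the same illustration, if the prior drug had raised QTcF, a true rise of 60 msec would read as 50 to 55 and miss the threshold. If it had lowered QTcF, a true rise of 50 to 55 msec could read as 60 and be counted.

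**The case against.** The strongest reply is that the trial has a concurrent randomised placebo arm and the plan compares ECG and laboratory changes with it. That stands. A reader might infer that the estimated study-drug effect is biased, but the documents do not support this: the washout component is common to both arms and cancels in expectation. What remains is mean-zero noise, smaller than the shared shift except at p = 10%, where the two are about equal (0.10w against an SD of 0.085w).

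A reader might also infer that these baselines are taken before the washout. The documents leave the order open, and split screening already permits a later ECG.

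Further points stand in part:
- **The affected group is narrower than all previously treated subjects.** Exclusion criterion 4 removes anyone with a positive urine drug screen at screening, and the panel (SAP Table 2) includes amphetamines. Read literally, that excludes most subjects still taking amphetamine-type treatment. The panel does not list methylphenidate, atomoxetine, tricyclics or guanfacine, all named in the protocol's rationale, so the group is reduced but not eliminated.
- **The mechanism is only suggested.** Shared norepinephrine reuptake inhibition says nothing about the size, direction or persistence of an ECG effect, and the documents offer no mechanism for laboratory values.
- **Some outputs do not depend on baseline.** These are the actual values and the count of QTcF at or above 500 msec. Prior medications and ECGs are also listed by subject. Vital signs have a Visit 2 measurement and are unaffected.

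These replies do not reach the within-treatment summaries, the shift tables or the 60-msec count, because randomisation does not correct an individual's own baseline.

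**Conclusion.** The point holds as a limited weakness in the safety summaries. The ECG and laboratory reference value is a screening-period value with no fixed position relative to the washout. For subjects withdrawn from treatment after consent, it can be on-drug or only partly washed out. Within-arm mean changes may then be off by p × w, and an individual change by up to w, in an unknown direction. The comparison with placebo is protected in expectation and keeps only added noise and chance imbalance at about 25 per arm.

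This rests on three things the documents do not settle: how many subjects enter on a drug the urine screen does not exclude, how large any washout shift is, and when sites actually take the screening ECG and blood. The 10% to 50% range and the 5 to 10 msec illustration are assumptions. The case for acting is that the remedy is cheap and the affected tables serve the primary objective.

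**What to change.** **In the SAP.** Flag subjects who were on ADHD treatment at the time of the screening ECG or laboratory test. Treatments ongoing at consent are already recorded (SAP 3.6.6). If stop dates are not available to compare with the test date, treatment ongoing at consent will serve as the flag. Show Tables 14.3.2.1 to 14.3.2.4 (laboratory summaries and shifts) and 14.3.5.2 to 14.3.5.4 (ECG change, ECG shift and QTcF outliers) with and without flagged subjects. This needs no new data and works even if enrolment is complete.

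**In the protocol, for subjects still to be screened.** Where screening is already split over visits, place the existing baseline ECG after the washout and before the first dose, with the laboratory tests too if central-laboratory turnaround allows. State that this value is the baseline.

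**Cost.** Second versions of seven tables (4 laboratory + 3 ECG), with small flagged subsets: 25 × 0.10 to 25 × 0.50, or about 3 to 12 subjects per arm on the assumed range. Scheduling becomes tighter, with about 4 days of slack in the 14-day window; ECGs are already reviewed within 24 hours (Protocol 9.4.4.6). A site that also wants an ECG before treatment is withdrawn would do one repeat ECG. No repeat laboratory draw is required.

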### 9.7.1.7. Other Special Tests

Findings from the physical examinations will be summarized through 2 by 2 shift tables that, for each system or area examined, compare the normal/abnormal finding at screening to the normal/abnormal finding at the Final Visit.

### 9.7.2. Sample Size and Power Considerations

Approximately 50 subjects (approximately 25 per treatment group) will be randomized in the study. The sample size is not based on any statistical considerations, but it was judged adequate to provide safety, PK, and efficacy information for a proof-of-concept study.

## 10. PROCEDURES AND INSTRUCTIONS

### **10.1. Ethics and Good Clinical Practice**

The Investigator agrees, when signing the protocol, to adhere to the instructions and procedures described in the protocol and to adhere to the principles of ICH GCP to which the protocol conforms as well as all governing local regulations and principles for medical research.

The protocol, informed consent, and appropriate related documents must be reviewed and approved by an IRB constituted and functioning in accordance with ICH E6, Section 3, and any local regulations, i.e. Federal Regulations, Title 21 CFR Part 56. Documentation of IRB compliance with the ICH and any local regulations regarding constitution and review conduct will be provided to the Sponsor.

A signed letter of study approval from the IRB Chairman must be sent to the Investigator with a copy to the Sponsor prior to study start and the release of any SM to the site by the Sponsor (or designee). If the IRB decides to suspend or terminate the study, the Investigator will immediately send the notice of study suspension or termination by the IRB to the Sponsor.

Study progress is to be reported to IRB annually (or as required) by the Investigator or Sponsor, depending on local regulatory obligations. If the Investigator is required to report to the IRB, he/she will forward a copy to the Sponsor at the time of each periodic report. SAEs should be reported to the IRB in accord with local regulatory requirements.

#### **10.2.** Subject Information and Informed Consent

As part of administering the informed consent documents, the Investigator (or designee) must explain to each subject the nature of the study, its purpose, the procedures involved, the expected duration, the potential risks and benefits involved, and any potential discomfort. Each subject must be informed that participation in the study is voluntary and that he/she may withdraw from the study at any time and that withdrawal of consent will not affect his/her subsequent medical treatment or relationship with the treating physician.

This informed consent should be given by means of a standard written statement, written in non-technical language. The subject should understand the statement before signing and dating it and will be given a copy of the signed document. If written consent is not possible, oral consent may be obtained if witnessed by at least one person not involved in the study. The verbal consent will be documented and signed by the Investigator and the witness(s). No subject can enter the study before his/her informed consent has been obtained.

A separate ICF will be given for the optional PK substudy. The above procedures will be followed in obtaining this consent.

#### **10.3.** Changes to the Protocol

There are to be no changes to the protocol without written approval from the Sponsor. The protocol will be followed as written.

Any change to the protocol requires a written protocol amendment or administrative change that must be approved by the Sponsor before implementation. Amendments specifically affecting the safety of subjects, the scope of the investigation, or the scientific quality of the study require additional approval by the applicable IRBs. These requirements should in no way prevent any immediate action from being taken by the Investigator, or by the Sponsor, in the interest of preserving the safety of all subjects included in the study. If an immediate change to the protocol is felt by the Investigator to be necessary for safety reasons, the Medical Monitor must be notified promptly and the IRB for the site must be informed promptly.

Changes affecting only administrative aspects of the study do not require formal protocol amendments or IRB approval, but the IRB must be kept informed of such changes. In these cases, the Sponsor will send a letter to the IRB detailing such changes.

#### **10.4.** Adherence to the Protocol

The Investigator will conduct the study in strict accordance with the protocol, which has been written to enable the Investigator's compliance with ICH E6, Section 4, "Investigator Guideline for Good Clinical Practices".

There are to be no Investigator-initiated deviations from the protocol. Any subject whose treatment deviates from the protocol or who is not qualified for study participation may be ineligible for analysis and may compromise the study. On occasion, a subject whose medical condition does not exactly conform to the specifications of the protocol but who could potentially benefit from study participation may be considered for enrollment by the Sponsor if the Investigator first reviews the situation with the Medical Monitor. In these cases, the potential subject's participation will be discussed with the Sponsor personnel prior to having the subject sign the informed consent, and the exemption for study enrollment will be sent in writing to the investigational site by the Sponsor. The investigational site will retain a copy of this document. If the Investigator learns at any time after informed consent that a subject does not meet protocol specifications for study participation, he/she will call the Medical Monitor immediately.

Subjects who have not signed an IRB approved ICF cannot receive SM.

The Investigator and research team must comply with ICH E6 principles and all applicable local regulatory laws and regulations.

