## 9.1.1. Screening Period

Screening will take place within 14 days prior to randomization to determine subjects' eligibility to participate in the study. No screening or study-specific assessments may be performed until written informed consent has been obtained. Screening procedures will be performed to determine each subject's eligibility to participate in the study and may be carried out over more than one visit during the Screening Period. Abnormal results on laboratory tests may be repeated once at the discretion of the Investigator during the Screening Period.

Additional screening procedures will include review of medical and psychiatric history, including confirmation of ADHD diagnosis and smoking history; assessment of suicide risk; assessment of demographic and baseline characteristics; full physical examination; measurement of vital signs, height and weight; ECG; sample collections for hematology, biochemistry, CYP2D6 enzyme activity screening, urinalysis, urine drug screen and serum pregnancy test (FOCP only); prior and concomitant medication information will also be collected.

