# 9.3.2 Exclusion Criteria

A subject will not be eligible for inclusion in this study if any of the following criteria apply:

- 1. Current or past history of psychotic disorder or major depressive disorder with psychotic features.
- 2. Presence of another primary DSM-IV-TR disorder.
- 3. Suicidality, defined as either active suicidal plan/intent or active suicidal thoughts in the 6 months before the Screening Visit or more than 1 lifetime suicide attempt. (The Columbia-Suicide Severity Rating Scales [C-SSRS] will be administered at each visit.)
- 4. Substance or alcohol abuse/dependence within previous 6 months, or a positive urine drug screen at screening or baseline prior to first dose of study medication (SM).
- 5. Any known or suspected significant medical or psychiatric illnesses that, in the judgment of the Investigator, may impair interpretation of study results or constitute a significant safety concern in the context of the clinical trial
- ECG abnormalities (clinically significant according to Investigator's opinion) or vital sign abnormalities (systolic blood pressure [SBP] <90 or >140 millimeters of mercury [mmHg], diastolic blood pressure [DBP] <40 or >90mmHg, or heart rate [HR] <40 or >100 beats per minute [BPM]) at screening.
- Clinically significant laboratory abnormalities; including presence of potential hepatic function impairment as shown by, but not limited to alanine aminotransferase (ALT) values >2 times upper limit of normal (ULN), aspartate aminotransferase (AST) > 2 times ULN, gamma-glutamyl transpeptidase (GGT) >3 times ULN, or total bilirubin >1.5 ULN.
- 8. Medications, including health food supplements judged by the Investigator to be likely to have central nervous system activity (for example, St John's Wort, gingko leaf, and melatonin), are not permitted during the study. If the subject is taking the medication prior to study entry, there must be a 7 day washout period prior to first dose of SM.
- 9. Lifetime history of tic disorder, Tourette's Disease, or organic brain disorder; or family history of Tourette's Disease.
- 10. Current or lifetime history of hyperthyroidism unless treated and stable for 6 months.
- 11. Participation in or plan to begin behavioral therapy during the study.
- 12. Subject has a prior history of allergy or any significant adverse reaction (including rash) to viloxazine, or any of the product components.

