### 9.5.5. Method of Assigning Subjects to Treatment Groups

The randomization for this study will be managed centrally; specific instructions to conduct subject randomization will be provided in a separate document to all investigational sites.

A randomization scheme will be generated using a pseudo-random number generator in a computer program. The method avoids bias by use of a chance mechanism. The randomization scheme assigns Treatment 1 or Treatment 2 to each randomization number in a 1:1 ratio.

Upon admission to the study, subjects will be assigned a 4-digit screening number, in the order that they are entered. Subjects who subsequently meet all eligibility criteria will be assigned a 6-digit randomization number. The first 3 digits will refer to the site, and the last 3 will refer to the subject-specific number, which will be assigned according to the randomization scheme.

Once a randomization number has been assigned, no attempt should be made to use that number again, if, for example, a subject is withdrawn. All subjects are randomized only once.

Note: all subjects who participate in the optional PK substudy will be given active SPN-812V capsule(s) in this portion.

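### Protocol 10.4 allows case-by-case sponsor exemptions that contradict the eligibility rules in 9.3 and 9.5.5, with no protection for safety exclusions and no rule for analysing exempted subjects

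*Protocol*

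**What the plan says.** Protocol 10.4 first bars deviations started by the Investigator and warns that an unqualified subject may be unusable for analysis and may compromise the study. It then opens a route for "a subject whose medical condition does not exactly conform to the specifications of the protocol but who could potentially benefit from study participation". Such a subject "may be considered for enrollment by the Sponsor if the Investigator first reviews the situation with the Medical Monitor". As to timing, 10.4 says that the case "will be discussed with the Sponsor personnel prior to having the subject sign the informed consent". If the sponsor agrees, it issues a written exemption, and the site keeps a copy.

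The eligibility text is unconditional. Section 9.3.1 admits subjects who meet all the inclusion criteria. Section 9.3.2 opens with: "A subject will not be eligible for inclusion in this study if any of the following criteria apply". Section 9.5.5 says: "Subjects who subsequently meet all eligibility criteria will be assigned a 6-digit randomization number", and SAP 3.3 repeats this. None of these sections refers to 10.4 or to an exemption.

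On timing, 9.1.1 states: "No screening or study-specific assessments may be performed until written informed consent has been obtained".

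**The concern.** Two parts of the same protocol answer the same question differently. A site that follows 9.3.2 and 9.5.5 cannot enrol and randomize a subject who meets an exclusion. A site holding a sponsor exemption under 10.4 is told that it can.

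Safety is the primary objective, and several exclusions remove subjects at higher risk. An exemption route that does not set those exclusions apart could bring in subjects whom 9.3 says are not in the trial. The safety results would then describe a population other than the stated one. The documents also leave open how such a subject is to be analysed.

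**Working it through.** No arithmetic bears on this point, so the check sets the sections side by side.

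1. **Who may enter.** Protocol 9.3.1 requires all inclusion criteria, and 9.3.2 makes one exclusion enough for ineligibility. Section 10.4 allows entry despite a non-conforming medical condition. As neither part of 9.3 mentions an exception, the texts conflict for any subject who is exempted.

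2. **Who may be randomized.** Protocol 9.5.5 and SAP 3.3 assign the randomization number after all criteria are met. The synopsis randomizes once eligibility is confirmed, and 9.1.2 has the criteria re-assessed at baseline. SAP 4.2 describes all randomized subjects as having met the requirements for participation. An exempted subject fails each of these as written.

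3. **What limits the exemption.** Section 10.4 asks for Investigator review with the Medical Monitor, sponsor agreement and a written record. It gives no maximum number, names no exclusion that must stand and requires no IRB review of the individual case.

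4. **Which criteria it can reach.** The exemption is discussed before consent (10.4), while screening assessments come only after consent (9.1.1).
   - The ECG and vital sign exclusion in 9.3.2 concerns findings at screening, so those findings do not yet exist when the exemption is discussed. The same holds for laboratory results obtained at screening.
   - Exclusions already known from history are within reach: seizures or seizure risk factors, tic disorder, past suicidality.
   - For a non-conformity learned after consent, 10.4 tells the Investigator to call the Medical Monitor immediately and states no outcome.

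5. **How the subject is analysed.**
   - Safety population (Protocol 9.7.1.1, SAP 4.2): every randomized subject who takes at least one dose, so an exempted subject who is dosed is in.
   - ITT population (same sections): a dosed subject with a baseline and at least one post-baseline efficacy assessment, so an exempted subject with these is in by definition.
   - SAP 4.6: subjects who violate the inclusion or exclusion criteria are listed as potential removals from ITT, to be examined at the blind data review (SAP 4.7). It does not separate a sponsor-approved exemption from an unplanned violation.

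   The same subject can therefore count for safety and be dropped for efficacy, and nothing prespecified settles which.

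**The case against.** The best defence reads 9.3 and 9.5.5 as the general rule and 10.4 as an express exception, lacking only a cross-reference. The wording of 10.4 suggests rare and minor departures, and enrolment is possible rather than automatic. Medical Monitor review and a written record are real safeguards. Departures would also be visible: SAP 4.2 lists eligibility violations for all randomized subjects in Listing 16.2.2, and SAP 4.6 brings violators to the blind data review. Because the exemption comes before randomization, it cannot systematically favour one arm.

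Much of this stands, and it narrows the point. It does not remove it. No text confines the exemption to minor departures or keeps it away from safety exclusions, 9.3 and 9.5.5 recognise no exception, and a listing does not tell the analyst how to classify the subject.

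A reader might infer four stronger things that the documents do not support.

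- *That 10.3 forbids the exemption.* Section 10.3 does say "The protocol will be followed as written", but 10.4 is part of the protocol, and the IRB approves the whole protocol before screening (5.1, 10.1). Using 10.4 is following the protocol. The gap is confined to IRB review of the individual case.
- *That every criterion can be waived.* The provision speaks of a medical condition. Contraception, planned behavioral therapy and recent use of an investigational drug are not medical conditions, and step 4 puts findings first made at screening largely out of reach.
- *That one exempted subject's share of an arm of about 25, set against the AE summary threshold, measures the harm.* That share is the same for any subject in the arm, so it reflects the sample size and says nothing about exemptions.
- *That medical details are disclosed to the sponsor without consent.* Section 10.4 says that participation is discussed; it does not say that identifiable information is passed on.

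**Conclusion.** The contradiction is real. Protocol 10.4 permits a written, case-by-case sponsor exemption that 9.3.1, 9.3.2 and 9.5.5 (with SAP 3.3) do not allow. It has no cap, no carve-out for safety exclusions and no case-level IRB step. Its practical reach is mainly exclusions known from history, and that set includes some with an evident safety purpose.

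The size cannot be put in numbers: the documents neither limit exemptions nor say how often they are expected. The consequence concerns whom the safety results describe and whether safety and efficacy rest on the same subjects; it is not a bias towards one arm. The conclusion assumes that 9.1.1 and the pre-consent timing in 10.4 are both applied as written. If exemptions were in practice also granted after consent, the reach would be wider. The point should be corrected, because safety is the primary objective and the correction is cheap.

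**What to change.** Reconcile Protocol 9.3.1, 9.3.2, 9.5.5 and 10.4. The simplest way is to delete from 10.4 the exemption provision and the sentences on its process: the pre-consent discussion, the written exemption and the site copy. Then state that no prospective exemptions from 9.3.1 or 9.3.2 are granted. If a criterion proves too strict, change it for all subjects by an amendment under 10.3 with IRB approval.

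If the sponsor keeps any exemption, limit it to criteria that are not safety exclusions and refer to it in 9.3 and 9.5.5. State in SAP 4.2 and 4.6 how an exempted subject is classified in the ITT and safety populations.

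The cost is one protocol amendment, plus a short SAP addition if an exemption is kept. An occasional borderline subject is lost, and recruitment may be slightly slower.
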